6.2 Arm 2: Active Control

The active control group will be comprised of 10 weekly 3-hour sessions of a *Living with HIV Support Group* held at the AIDS Committee of Toronto (ACT). This support group will be facilitated by a certified social worker and a peer (i.e., person aging with HIV). These groups use a model of mutual aid to encourage peer-based discussion on the effects of living with HIV. Topics are determined by the group; facilitators ensure that safety is maintained throughout and make connections between participants as appropriate. This model is the standard of group therapy for people with dementia (Toms, Clare, Nixon, & Quinn, 2015) and is also frequently used for people living with HIV community-based service organizations in Ontario.

7. RISKS AND PRECAUTIONS

7.1 Risk Management

There is potential for research participants/group members to expose sensitive information about the group and/or other group members. Research participants/group members will be asked during the consent process and throughout the group sessions to maintain the confidentiality of the group, however group members are not bound by professional obligations to maintain the confidentiality of the group. Facilitators are bound by professional obligations to maintain the confidentiality of the group. The potential exposure of sensitive information will be highlighted in the consent form, and research participants/group members will be advised to practice some caution before sharing personal and sensitive information. Participants will only be referred to by a first name, and will be offered the possibility of using a pseudonym in group.

Research participants/group members may also experience discomfort and/or unease with discussion topics that emerge in the group context. Throughout the group sessions, the co-facilitators will debrief with research participants/group members and offer them opportunities to discuss any discomfort one-on-one. Research participants/group members will also be provided with information related to other counselling and support services available to them.

In terms of legal risk, participants will be informed of the standard limits of confidentiality during the consent process (harm to self or other, neglect or abuse of a minor, abuse by a regulated health professional). Co-facilitators will follow all legal requirements, in adherence with the policies set out by the agencies participating in this project.

7.2 Mental Health Support

A list with crisis centres, counselling options, and emergency supports will be provided to participants. Participants will also be informed that they are welcome to avail themselves of free, confidential counselling at the AIDS Committee of Toronto (ACT) by a counsellor unrelated to the study team.

8. CLINICAL EVALUATIONS

8.1 Questionnaires

For all questionnaires, the coordinator will be provided with a script so that they do not bias the answers. Baseline, Follow-Up, and End of Study questionnaires (as identified in Table 1) will be completed on a tablet or computer, unless the participant prefers a paper version, with the research coordinator assisting the participant with understanding questions and selecting responses. The group

satisfaction questionnaire in sessions 5 & 10 will be completed on paper. This questionnaire will contain the scale identified in Table 1, and will be complemented by questions regarding satisfaction with session, length, content, and feedback on the facilitators.

The stress, anxiety, mindfulness, and coping questionnaires will be completed electronically on a tablet or computer by the participant with the research coordinator's assistance at baseline, post-therapy, and 3-month follow-up. These questionnaires can be completed on paper and entered into the database by the research coordinator if requested by the participants

The Helping Characteristics of Self-Help and Support Groups Measure will be completed on paper by participants in the fifth and in the final session of their group therapy.

- **Appendix I:**
 - HIV/AIDS Stress Scale (29 items, Likert, $\alpha = 0.76-0.85$) (Packenham & Rinaldis, 2002).
- **Appendix II:**
 - Anxiety in Cognitive Impairment and Dementia (Gerolimatos et al., 2015)
- **Appendix III:**
 - Helping Characteristics of Self-Help and Support Groups Measure (20 items, Likert, $\alpha = 0.79-0.87$)
- **Appendix IV:**
 - Five Facet Mindfulness Questionnaire – Short Form (FFMQ-SF) (24 items, Likert, $\alpha = 0.73-0.91$)
- **Appendix V:**
 - Coping Self-Efficacy Scale of Health Problems (10 items, Likert, $\alpha = 0.779$) (Gandoy-Crego et al., 2016)

9. STUDY PROCEDURES

9.1 Schedule of Events

Table 1: Schedule of Events

Study Period	Screening Period			Study Period (Facilitator meeting & 10 weekly, 3-hour sessions)			Follow-up Period	
	Visit Name	Screening Call	Screening Visit	Baseline Visit	Facilitator meeting	Sessions 1-9	Sessions 5 & 10	Follow-up Visit
Visit No.	-3	-2	-1	0	1,2,3,4,6,7,8,9	5 & 10	11	12
Week No.			-1		1-10		11	23
Day No.	-56 to -7 days		-7		1-70		77	167
Visit Window	+/- 7	+/- 7	+/- 7	+/- 7	+/- 0	+/- 0	+/- 7	+/- 7
Procedures:								
Written Informed Consent		X						
Entry Criteria Assessment	X	X						
Chart abstraction		X						

(demographics, medical history, medications)								
Randomization			X ²					
Group Session (CRGT or Control)				X ³	X	X		
Weekly Session Report ¹					X	X		
Helping Characteristics of Self-Help and Support Groups Measure Questionnaire						X		
HIV/AIDS Stress Scale			X				X	X
Anxiety in Cognitive Impairment and Dementia Scale			X				X	X
Coping Self-efficacy of Health Problems Scale			X				X	X
Five Facet Mindfulness Questionnaire – Short Form (FFMQ-SF)			X				X	X

¹ Completed by therapy facilitator

² To occur once all participants have been enrolled and eligibility confirmed

³ Acquaintance with group only; no therapy will be administered during this session

9.2 Screening Period Procedures/Assessments

9.2.1 Screening Call [Visit no. -3]

The research coordinator will phone the participant to:

- Describe the study
- Review entry criteria
- Schedule a time to meet for the Screening Visit

It is expected that this call will be approximately twenty (20) minutes.

9.2.2 Screening Visit [Visit no. -2]

The following activities will occur at the Screening Visit:

- The Informed Consent Form will be reviewed with the participant
- The participant will be asked to sign the consent form

- The participant's availability to participate in a 10-session group will be ascertained (e.g., preference for afternoons, time of day)
- The participant's ability to access a mobile device (i.e., smartphone or tablet) will be determined

It is expected that this visit will be approximately thirty (30) minutes.

After the Screening Visit and if the participant has signed in the Informed Consent Form, the research coordinator will conduct a chart review to abstract demographics, medical history, and medications. This chart abstraction will confirm entry criteria.

9.2.3 Baseline Visit [Visit no. -1]

The following activities will occur at the Baseline Visit:

- The participant will be asked to complete the following study questionnaires:
 - HIV/AIDS Stress Scale
 - Anxiety in Cognitive Impairment and Dementia Scale
 - Coping Self-efficacy of Health Problems Scale
 - Five Facet Mindfulness Questionnaire – Short Form
 - Two brief questions on use of brain training activities

The Baseline Visit will take approximately thirty (30) minutes to complete.

9.3 Study Period Procedures/Assessments

9.3.1 Study Arms

Arm 1 (Experimental Therapy): CRGT will be facilitated by an MBSR-certified social worker and a peer (i.e., person aging with HIV). The peer will lead facilitation of the brain training exercise, which will comprise one-third of each group session. Brain training exercises will be delivered on tablets using PositScience software by BrainHQ. This software tailors participant experience based on deficit domains. Participants will work through activities and support one another through their strengths and weaknesses. The social worker will lead facilitation of the MBSR component, which will comprise the remaining time of each session. MBSR involves activities such as meditation and breathing exercises to achieve emotional regulation.

Arm 2 (Active Control): The active control group will be facilitated by a social worker and a peer. These groups use a model of mutual aid to encourage peer-based discussion on the effects of living with HIV. Topics are determined by the group; facilitators ensure that safety is maintained throughout and make connections between participants as appropriate.

9.3.2 Facilitator Meeting [Visit no. 0]

The Facilitator meeting in both study arms will include a preliminary meeting with the experimental therapy and active control facilitators to acquaint themselves to the upcoming group prior to the first session. This will take approximately 20 minutes and will take place at the therapy site (**arm 1 (Experimental):** Toronto General Hospital; **arm 2 (Active Control):** ACT).

9.3.3 Therapy Sessions 1, 2, 3, 4, 5, 6, 7, 8, 9 & 10 [Visit no. 1, 2, 3, 4, 5, 6, 7, 8, 9, & 10]

During these visits all participants will attend the three-hour sessions as described above during ten consecutive weeks.

After each visit, the therapy facilitator will complete a weekly session report.

At the conclusion of visits 5 & 10, the following activity will occur:

- Participants will be asked to complete the “Helping Characteristics of Self-Help and Support Groups Measures” questionnaire.

This questionnaire will take approximately ten minutes to complete.

9.4 Follow-up Period Procedures/Assessments

9.4.1 Follow-up Visit [Visit no. 11]

The participant will be asked to complete the following study questionnaires:

- HIV/AIDS Stress Scale
- Anxiety in Cognitive Impairment and Dementia Scale
- Coping Self-efficacy of Health Problems Scale
- Five Facet Mindfulness Questionnaire – Short Form
- Two brief questions on use of brain training activities

This visit will take approximately thirty (30) minutes to complete.

9.5 End of Study Visit [Visit no. 12]

The participant will be asked to complete the following study questionnaires:

- HIV/AIDS Stress Scale
- Anxiety in Cognitive Impairment and Dementia Scale
- Coping Self-efficacy of Health Problems Scale
- Five Facet Mindfulness Questionnaire – Short Form
- Two brief questions on use of brain training activities

This visit will take approximately thirty (30) minutes to complete.

9.6 Early Termination

If a participant cancels participation in the study, the research coordinator will attempt to follow-up with them to determine the reason for cancellation. These reasons will be described to inform the feasibility and acceptability outcomes.

10. STATISTICAL CONSIDERATIONS

10.1 General Study Design

This study is primarily focused on feasibility, acceptability, and intervention fidelity. Feasibility and acceptability will be analyzed using descriptive statistics (# of attendees, % satisfaction, etc.). Intervention fidelity will be analyzed qualitatively regarding how closely the facilitators adhered to their intervention model.

10.2 Sample Size Considerations/Justification

A sample size of 16 participants (8 in each study arm) has been selected as: (a) 8 participants has been found to be an ideal size for a 10-week group therapy intervention (Stewart, Usher, & Allenby, 2009; Erickson, 1982; Weis, 2003); and (b) this number will provide preliminary insight into the acceptability of novel CRGT arm, which will be important to consider before the larger RCT is initiated. This sample size has also been selected for feasibility: 16 qualifying participants can be feasibly enrolled in the pilot given the number of qualifying participants available for sampling from the patients tested for HAND at St. Michael's Hospital Neurobehavioral Research Centre (N=~100). It is expected that this sample can be enrolled in a 2-month period.

10.2.1 Efficacy: Intent-to-Treat

The intent-to-treat (ITT) data set will include data from all randomized participants. All data will be included and no participants excluded because of protocol deviations. The proportion of patients who consented to participate and who actually participated will be described against the total number of patients contacted.

10.3 Analysis of Demographic and Baseline Data

Demographics will be described, to provide characteristics (i.e., gender, age, ethnicity, sexual orientation) of participants in this pilot study.

10.4 Analysis of Primary Outcome Measures

Feasibility and acceptability results will be reported against the targets specified in Section 2.2 of this protocol.

10.5 Analysis of Secondary Outcome Measures

The sample size severely limits any statistical procedures for analyzing change in stress, anxiety, and coping. Depending on the nature of the results (and the true sample size), non-parametric tests or a power analysis may be appropriate.

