Exploratory Objectives	
 1. Change in stress, anxiety, and coping from pretest to posttest (between groups) 2. Sustained use of brain training activities 3. Change in use of mindfulness strategies (between groups)
Sample Size	N = 16
Randomization	1:1 8 in the treatment group and 8 in the active control group
Study Population	HIV-positive people \geq 40 years of age who have been living with HIV for more than 5 years and who have completed neuropsychological testing, received a diagnosis of Mild Neurocognitive Disorder (MND)
Experimental Therapy Description	Cognitive remediation group therapy: 10 weekly 3-hour sessions; each session is comprised of 45 minutes of tablet-based cognitive training using PositScience, a 15-minute break, and 1.75 hours of Mindfulness-Based Stress Reduction (MBSR) with a 15-minute break halfway through the MBSR component.
Active Control	10 weekly 3-hour sessions with a 15-minute break at the end of each hour; each session is comprised of process-oriented facilitation using a mutual aid model (i.e., encouraging peer discussion of effects of HIV, aging, and cognitive impairment to identify and initiate coping strategies).
Duration of Study	Ten weeks
Outcome Measures	
Primary:
 
Feasibility: The sampling frame is approximately 100 people. The following targets (all based on a denominator of 100) would need to be met for a larger study to be considered feasible: $\geq 30\%$ of those contacted agree to participate, $\geq 25\%$ complete the pre-test, $\geq 20\%$ attend the first session, $\geq 16\%$ complete the full series and complete the post-test. Each participant must attend 80% (8/10) of the group sessions to be considered as completing the series.

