2.4 Exploratory Objectives

- To evaluate the change in stress, anxiety, and coping.
- Sustained use of brain training activities
- Change in use of mindfulness strategies

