3. SELECTION AND ENROLLMENT OF PARTICIPANTS

3.1 Number of Participants

A total of 16 participants (8 in each study arm) will be enrolled.

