3.7 Sampling and Recruitment

There are approximately 100 people currently in the sampling frame (see Appendix V). This should provide an adequate frame to recruit participants ($n = 16$), especially as there is little other treatment

available for HAND in Toronto (or elsewhere). We will initiate the trial with a minimum of 75% participant enrolment (n = 12, with n = 6 in the Experimental arm and n = 6 in the Active Control arm) if required.

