5. RANDOMIZATION PROCEDURE

5.1 Randomization

Once enrollment is complete and all participants have consented to take part in the study and been screened for entry criteria, and attended the Screening Visit and Baseline Visit, the research coordinator will contact the CTN to request randomization assignments. Participants will be randomly assigned to one of the two study arms (Arm 1 = Experimental or Arm 2 = Active Control) using random numbers in blocks of size two. Randomization will be performed in a 1:1 fashion to allow for equal numbers of participants in both arms.

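### The exploratory between-arm comparison is framed as pretest-to-posttest change, and the plan does not say that the Baseline score will be used as a covariate

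*Combined protocol and SAP*

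**What the plan says.** The Protocol Synopsis gives the first exploratory objective as "Change in stress, anxiety, and coping from pretest to posttest (between groups") and describes change in use of mindfulness strategies as a between-group question too. Section 2.4 has the shorter "To evaluate the change in stress, anxiety, and coping".

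Section 10.5 is headed as secondary outcomes but deals with these exploratory scales. It states that "The sample size severely limits any statistical procedures for analyzing change in stress, anxiety, and coping", and then that, depending on the results and the sample size achieved, "non-parametric tests or a power analysis may be appropriate". The Statistical Analysis row of the synopsis says much the same. Neither place names an estimator, a model, a covariate or a confidence interval, and 10.5 does not mention mindfulness.

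Table 1 in section 9.1, with sections 8.1, 9.2.3, 9.4.1 and 9.5, schedules the stress, anxiety, coping and mindfulness scales at Baseline, Visit 11 and Visit 12. Section 3.1 sets the size: "A total of 16 participants (8 in each study arm) will be enrolled". Section 3.7 allows a smaller start ("We will initiate the trial with a minimum of 75% participant enrolment"), which is 6 per arm. Section 5.1 allocates "using random numbers in blocks of size two", with no stratification by baseline score.

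**The concern.** Blocks of two equalise the arm sizes but do nothing to equalise the scores. With 6 to 8 people per arm, sizeable baseline differences will often arise by chance. People who start high tend to drift down and people who start low tend to drift up, so a raw change score carries part of the baseline difference into the treatment contrast with its sign reversed. A rank test on change scores depends on baseline in the same way.

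The stake is modest but real. Section 1.3 gives determining the sample size of a full-scale trial as one purpose of the pilot, and both the synopsis and 10.5 contemplate a power analysis on these outcomes. A baseline-adjusted model would supply the residual SD and baseline slope for that work. In addition, 10.5 lets the method depend on the nature of the results. As written, the choice between change, follow-up score and adjusted score could therefore be made after the baseline imbalance is visible.

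**Working it through.** **The plan's own figure.** N = 2 x 8 = 16 rests on therapy-group size and recruitment feasibility (section 10.2). No alpha, power, effect size, SD or correlation is given, so there is no power calculation to reproduce. The minimum start is 0.75 x 16 = 12, or 6 per arm.

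**Assumptions.** Scores are in SD units with equal SD at both times and independent participants. The correlation r is not in the documents, so a range is shown. n is the number per arm and N = 2n.

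**Step 1: size of chance imbalance.** The baseline mean difference D has SD sqrt(2/n).
- n = 8: sqrt(2/8) = 0.50, so P(|D| > 0.5) = P(|Z| > 1.00) = 32%.
- n = 6: sqrt(2/6) = 0.577, so P(|D| > 0.5) = P(|Z| > 0.866) = 39%.

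**Step 2: what passes into the change score.** Given D, the expected follow-up difference is the true effect plus rD. Subtracting D leaves the true effect minus (1 - r)D. For D = 0.5 the shift is:
- r = 0.3: 0.7 x 0.5 = 0.35 SD
- r = 0.5: 0.5 x 0.5 = 0.25 SD
- r = 0.7: 0.3 x 0.5 = 0.15 SD
- r = 0.9: 0.1 x 0.5 = 0.05 SD

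Simulation agrees (40,000 trials per setting). At n = 8 and r = 0.5, trials with D above 0.5 had a mean D of 0.76. With no true effect, the change-score contrast averaged -0.385, against an expected -(0.5 x 0.76) = -0.38. The baseline-adjusted contrast averaged -0.005.

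**Step 3: precision.**
- Var(change) = 2(1 - r)(2/n)
- Var(adjusted) = (1 - r^2)(2/n)[1 + 1/(N - 4)], where the bracket is the cost of estimating the slope
- Ratio, adjusted to change = [(1 + r)/2][1 + 1/(N - 4)]
- 95% half-width = t x sqrt(Var), with N - 2 df for change and N - 3 df for adjusted

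| r | 8 per arm: variance ratio | 8 per arm: half-width, change / adjusted | 6 per arm: variance ratio | 6 per arm: half-width, change / adjusted |
|---|---|---|---|---|
| 0.3 | 0.70 | 1.27 / 1.07 | 0.73 | 1.52 / 1.32 |
| 0.5 | 0.81 | 1.07 / 0.97 | 0.84 | 1.29 / 1.20 |
| 0.7 | 0.92 | 0.83 / 0.80 | 0.96 | 1.00 / 0.99 |
| 0.8 | 0.98 | 0.68 / 0.68 | 1.01 | 0.81 / 0.83 |
| 0.9 | 1.03 | 0.48 / 0.49 | 1.07 | 0.58 / 0.60 |

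**Step 4: break-even.** On variance alone, (1 + r)/2 = 12/13 gives r = 0.85 at 8 per arm, and 8/9 gives r = 0.78 at 6 per arm. Interval width also pays for the lost degree of freedom:
- 8 per arm: (t13/t14)^2 = (2.160/2.145)^2 = 1.015. Then (1 + r)/2 = 1/(1.083 x 1.015), so r is about 0.82.
- 6 per arm: (t9/t10)^2 = (2.262/2.228)^2 = 1.031. Then (1 + r)/2 = 1/(1.125 x 1.031), so r is about 0.72.

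**Step 5: power, for scale only.** For an assumed 0.8 SD effect at r = 0.5 (two-sided 5%), power is 32% with change and 38% with adjustment at 8 per arm, and 24% and 27% at 6 per arm.

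**The case against.** The strongest answer is that the plan commits to no method. A reader might infer from the synopsis that an unadjusted change-score analysis is planned and that the Baseline score will be used only by subtraction. The documents do not say so. The synopsis words an objective, and 10.5 names no estimator. An objective about change is also compatible with adjustment, because regressing change on arm and baseline gives the same arm effect as regressing follow-up on arm and baseline. This stands: the gap is an omission, and the shift in step 2 is what follows if the wording is taken literally.

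Three further inferences also fail.
- *The change score is biased.* Over repeated randomisations it is not. The shift is conditional on the baseline difference observed in this one trial.
- *The change score always has the wider interval.* That depends on r, and the table shows the reverse at high r.
- *These scales are the only between-arm information the pilot will produce.* The primary objective itself compares feasibility and acceptability with the control. The satisfaction measure is completed at sessions 5 and 10, and both arms file fidelity reports.

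It is also fair to say that little depends on the answer. Section 10.1 puts the focus on feasibility, acceptability and fidelity, no hypothesis test is committed, and none of the three papers listed in section 13 is an efficacy paper. Section 10.5 already concedes that the sample is too small for much. Finally, sections 6.1 and 6.2 give each arm its own site and facilitators, and 8 per arm is a single therapy group. Group effects are therefore confounded with arm, and baseline adjustment cannot change that.

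These points lower the severity. They do not remove the case for saying, before the data are seen, how the Baseline scores will be used.

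**Conclusion.** The point holds as a low-severity omission. The between-arm question is worded as change, the only analysis contemplated is a possible non-parametric test or power analysis, and the Baseline score is nowhere named as a covariate although it is collected for all four scales.

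Taken literally, the wording exposes the result to (1 - r) of a baseline difference that will often be large at this sample size. The sizes in steps 1 and 2 assume equal SDs, independent participants and a correlation the documents do not give. Removing that conditional shift is the main gain from adjustment. The precision gain is secondary: useful at r of 0.5 or below, small at 0.7, and gone above about 0.82 (8 per arm) or 0.72 (6 per arm). The comparison stays underpowered either way, and the feasibility decision is untouched.

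**What to change.** Add to section 10.5 that any between-arm estimate for stress, anxiety, coping or mindfulness at Visit 11, and separately at Visit 12, will come from a linear model with arm and the same scale's Baseline score, reported descriptively with a 95% confidence interval. State that any rank-based analysis will also use the ranked Baseline score as a covariate. State that the interval is conditional on the single therapy group delivered in each arm.

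The cost is a sentence or two of text and one degree of freedom. No new data are needed, because section 5.1 places randomisation after the Baseline Visit, and N does not change. The downside is that precision does not improve if r is high. At r = 0.9 the half-width goes from 0.48 to 0.49 SD at 8 per arm and from 0.58 to 0.60 SD at 6 per arm.
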